6.1.2 Intervention

On the day following surgery (postoperative day 1) at 9:00 am, the nurse will perform the corresponding intervention operations for patients in both groups based on the group assignment indicated in the randomization envelope. Before the intervention, both groups of patients must complete the CRBD (Catheter-Related Bladder Discomfort) grading assessment by the assigned nurse (Appendix 3). During the patient's first catheterization, the use of selective α 1-adrenergic receptor blockers (such as tamsulosin) is not permitted.

1) The ICCAUT strategy included intermittent urethral catheter clamping and active urination training. In the ICCAUT group, intermittent catheter clamping was initiated at 9:00 am on the first postoperative day. In each cycle, the catheter was clamped for 3 h, followed by a 5-min release. The next cycle began as soon as the previous cycle had been completed. Catheter training concluded at 10:00 pm on the first postoperative day, and the catheter was left open during the night. The urinary catheter was removed on the second postoperative day, and the training did not stop until the catheter had been removed. During the training period, if the patient experienced a strong urge to urinate before the 3-h clamping time was over, the clamping could be released in advance for 5 min, allowing the patient to proceed to the next cycle of bladder training. Each time the catheter was released, the patients were encouraged to actively initiate urination to facilitate complete bladder emptying. We refer to this catheter management strategy, which involves intermittent clamping of the catheter and active urination during the release periods, as the ICCAUT

management strategy.

2) For patients in the free-draining group, no intervention was performed using a catheter during this period. The urinary catheter was removed at 9:00 am on the second postoperative day.

3) Before the urinary catheter is removed on the second day, both groups of patients must complete the CRBD (Catheter-Related Bladder Discomfort) grading assessment again by the assigned nurse (Appendix 3), and urine samples must be collected for urinalysis and urine culture. Additionally, patients in the ICCAUT group must scan a code to fill out the Bladder Training Quality Self-Assessment Form (Appendix 4) before the catheter is first removed. After the catheter is removed, the time from the first catheter removal to the first urination, as well as the volume of the first urination, should be recorded for both groups of patients.

4) Immediately after the first urination, a bladder ultrasound must be performed to assess the residual urine volume in the bladder. The bladder ultrasound is conducted by a fixed radiologist from the ultrasound imaging department, who is exclusively assigned to our department and is located in the same therapeutic area as the patient. After the urinary catheter is removed, the patient must be observed and the situation of any secondary catheterization must be recorded. The observation period is the following 7 days after first urinary catheter removal. For patients who undergo secondary catheterization, the time from the first catheter removal to the secondary catheterization, the volume of urine drained after secondary catheterization, the method of secondary catheterization, and the reason for secondary catheterization must be recorded.

5) Record the IPSS score and ICIQ-SF score of the patient on the day following the first catheter removal (excluding patients who underwent secondary catheterization). Record complications within 30 days after surgery and their Clavien-Dindo classification (Appendix 5).

6.1.3 Discharge and follow-up.

After discharge, when the patient returns for a follow-up visit one month after

surgery, the physician must collect information on complications and their grading within the first postoperative month, and conduct an assessment using the one-month postoperative urinary function score form.

Table 1: Study Enrollment, Intervention, and Outcome Assessment Form

Item	Time point	Study phase		
		Surgery and Recruitment randomization		Post-randomization
		t	n	
Enrollment:				
Screen suitable population			X	
Informed consent			X	
Baseline and surgery-related data collection		X		X
Randomization			X	
Intervention:				
ICCAUT group				X
Free-drainage group				X
Assessment:				
Bladder residual urine volume and secondary catheterization record				X
Record of information after catheter removal				X
Catheter-related bladder discomfort (CRBD) grading assessment				X
Bladder training self-assessment form				X
Urinalysis and urine culture		X		X

Urinary function assessment	X	X	X
Postoperative complications and grading		X	X

6.2 Concomitant treatment, follow-up

The total follow-up time for postoperative patients is one month. The follow-up content includes postoperative complications within 30 days, as well as the IPSS and ICIQ-SF scores at one month postoperatively.

The follow-up within the first 30 days after surgery is conducted through in-hospital observation, outpatient visits, phone calls, or questionnaires.

Complications related to the surgery and their grading, as well as the solutions, are recorded during this period

The postoperative chemotherapy regimen for patients will be based on the NCCN 2023 Rectal Cancer Treatment Guidelines, which will guide the appropriate chemotherapy or systemic treatment.

6.3 Patient compliance and withdrawal

If, after randomization, a patient refuses the randomly assigned urinary catheter management method at any time during the indwelling urinary catheter period and requests to have the intervention carried out according to the other urinary catheter management method, the other urinary catheter management method shall be provided to the patient in accordance with the patient's wish. If at any time during the entire study, a patient requests to withdraw from the study, the principal investigator shall communicate with the patient to avoid disrupting the balance of the randomization due to the withdrawal. If necessary, the patient's compensation shall be increased. If the patient still insists on withdrawing from the study and refuses to allow the use of personal data in this research project, the patient shall be withdrawn from the study according to the patient's wish, and all data of this patient shall be treated as missing data. During the follow-up phase of the primary endpoint, if a

patient refuses to cooperate with the follow-up of the primary endpoint, including the follow-up of secondary catheterization and the assessment of residual urine volume, the principal investigator shall communicate with the patient and appropriately increase the compensation for the subjects to avoid the absence of the primary endpoint. If the patient stubbornly refuses to cooperate with the follow-up of the primary endpoint, the primary endpoint of the patient shall be treated as missing data, and other data shall be recorded in the database.

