11.3 Missing data and its handling approaches

11.3.1 Definition of Missing Data

Since the primary endpoint is a composite endpoint, if a patient fails to achieve any of the positive events within the primary endpoint (secondary catheterization or residual urine volume > 100 ml) and any of the following situations occurs: 1) the residual urine volume after the first urination following the removal of the urinary catheter is missing; or 2) the situation of secondary catheterization within 7 days after the removal of the urinary catheter is missing, the primary endpoint will be defined as missing. The possible reasons for the missing primary endpoint include: 1) loss to follow - up or death, making it impossible to know whether secondary catheterization occurs within 7 days after the removal of the urinary catheter; 2) after the removal of the urinary catheter, due to various reasons, the bladder ultrasound for assessing the residual urine volume after the first urination is not carried out in a timely manner; 3)

the patient refuses the researcher to use the data related to the patient's own micturition function.

In the case where a subject refuses the researcher to use their personal data, that is, the subject requests to withdraw the informed consent and drop out of this study midway, all the data of this patient will be treated as missing data in the ITT analysis. If the subject refuses the collection of research data after withdrawal but consents to the collection of data before withdrawal, the researcher will treat the data after withdrawal as missing values, and the data before withdrawal can be included in the analysis.

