11.3.2 Methods for handling missing data

In this study, if the missing rate of the primary endpoint is less than 5%, no imputation of missing data will be done in the analysis of the primary endpoint in the ITT, PPA, and ATA sets. During the analysis of the primary outcome, missing data will be treated as censored.

If the missing rate of the primary endpoint is 5% or higher at the end of the study, the following procedures will be adopted to handle the data with missing values in any variable of the primary endpoint.

- 1) When the data on post-void residual urine volume (RUVR) by ultrasound after the first urination is complete, and the situation of secondary catheterization within 7 days after the removal of the urinary catheter is also complete. There is no missing data.
- 2) When the data on post-void RUV by ultrasound after the first urination is complete, but the situation of secondary catheterization within 7 days after the removal of the urinary catheter is missing.

If the post-void RUV by ultrasound after the first urination is greater than 100 ml, handling method: The primary endpoint is reached (positive), and no imputation of missing data for secondary catheterization is performed.

If the post-void RUV by ultrasound after the first urination is less than or equal to 100 ml, handling method: Multiple imputation method is used to impute the

missing data of secondary catheterization.

3) When the data on post-void RUV by ultrasound after the first urination is missing, but the situation of secondary catheterization within 7 days after the removal of the urinary catheter is complete.

If secondary catheterization occurs within 7 days after the removal of the urinary catheter, handling method: The primary endpoint is reached (positive), and no imputation of missing data for RUV is performed.

If secondary catheterization does not occur within 7 days after the removal of the urinary catheter, and the post-void RUV by ultrasound after the second urination is not missing, handling method: The Last Observation Carried Forward (LOCF) method is used to impute the missing data of the first residual urine volume. In LOCF method, the post-void RUV after the second urination is used to impute missing data of the first post-void RUV.

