OR	odds ratios
SAP	statistical analysis plan
FD	free-drainage
LAR	low anterior resectio
RUV	residual urine volume
LOCF	Last Observation Carried Forward
ISR	intersphincteric resection
TCA	Turnbull-Cutait Pull-Through Coloanal Anastomosis
TaTME	total mesorectal excision
ARD	absolute risk differences
CRM	Circumferential Resection Margin
pCR	pathological complete response
DRM	Distal Resection Margin

1 Introduction

The ICCAUT trial is a single - center, prospective, two - arm, parallel - group randomized controlled study. It aims to investigate the effect of the intermittent catheter clamping combined with active urination training (ICCAUT strategy) on urinary retention and secondary catheterization after proctectomy. The aims, hypotheses, and design of the ICCAUT trial are detailed in the protocol. This statistical analysis plan (SAP) focuses on the upcoming analysis and presentation of the trial data. This SAP is based on the study protocol version 2.0. The comprehensive study design, including primary and secondary endpoints, methods for determining sample size, and the approach to data management, are essential parts of the SAP. They are crucial for understanding the trial's methodology and result interpretation.

We develop this statistical analysis plan before completing the enrollment. This helps avoid issues like selection bias in analysis methods and multiple comparisons. These issues could occur if the plan is not determined in advance.

2 Study description

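### Protocol 6.3 sets the primary endpoint to missing after refusal of follow-up, with no exception for an event already observed; 11.3 and the SAP count that event

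*Protocol*

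**What the plan says.** Protocol version 2.0, section 6.3, covers a patient who "refuses to cooperate with the follow-up of the primary endpoint, including the follow-up of secondary catheterization and the assessment of residual urine volume". If persuasion and extra compensation fail, "the primary endpoint of the patient shall be treated as missing data, and other data shall be recorded in the database". A separate sentence in 6.3 deals with patients who withdraw and refuse any use of their data, so the quoted rule concerns patients who decline follow-up only.

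Section 11.3.1 is narrower. The endpoint is missing only "if a patient fails to achieve any of the positive events within the primary endpoint" and, in addition, one of the two components is unknown. For a patient with a residual above 100 ml and unknown catheterisation status, item 2 of section 11.3.2 says: "The primary endpoint is reached (positive), and no imputation of missing data for secondary catheterization is performed". Item 3 treats a recorded secondary catheterisation with a missing residual in the same way. For a patient who withdraws but allows use of earlier data, 11.3.1 says "the researcher will treat the data after withdrawal as missing values, and the data before withdrawal can be included in the analysis".

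SAP 6.3.1 and 6.3.2 repeat the 11.3 rules and do not carry the 6.3 rule. The SAP states: "This SAP is based on the study protocol version 2.0". Neither document says which rule prevails.

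**The concern.** The two components become known at different times. Under section 6.1.2 the residual is measured immediately after the first void, while secondary catheterisation is observed for 7 days after removal. A patient can therefore meet the endpoint on the first void and decline the rest. Section 6.3 calls that endpoint missing; 11.3 and the SAP call it an event.

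The ordering is also odd. A patient who withdraws from the study but permits use of earlier data keeps that data under 11.3.1, whereas a patient who only declines further follow-up loses the endpoint status under 6.3.

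Three things depend on the coding: whether an observed event enters the primary analysis, the missing rate that decides whether imputation is used, and the all-negative sensitivity analysis (protocol 11.4.2.1, SAP 6.5.2.1), which would turn an observed event into a non-event. Below 5% missing nothing is imputed ("During the analysis of the primary outcome, missing data will be treated as censored"). The item 2 and item 3 rules sit in the branch for 5% or more, so below 5% the definition in 11.3.1 is what protects the event, and 6.3 contradicts that definition.

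**Working it through.** **Inputs.** Planning rates 59.3% (free drainage) and 44.7% (ICCAUT), 200 per arm, 400 in total (protocol 11.1); 5% imputation threshold (protocol 11.3.2). These inputs reproduce the plan's size: with two-sided 5% and 80% power, (1.960 + 0.842)² × (0.593 × 0.407 + 0.447 × 0.553) / 0.146² = 179.9, so 180 per arm, and 180/0.90 = 200. The conflict does not affect this figure. The number of refusers is not given and is assumed throughout.

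**Step 1: the same patient under each rule** (follow-up refused, data use not refused).

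| Known before refusal | Protocol 6.3 | Protocol 11.3 and SAP 6.3 |
|---|---|---|
| Residual 150 ml, catheterisation unknown | Missing | Event |
| Secondary catheterisation recorded | Missing | Event |
| Residual 100 ml or less, catheterisation unknown | Missing | Missing |

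The rules differ only where an event was already seen.

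**Step 2: the 5% trigger.** 5% of 400 is 20. Assume 10 patients per arm refuse after the residual is known, at the planning rates, with every event visible by then. Under 6.3, 20/400 = 5.0% are missing and imputation applies. Under 11.3, the expected number missing is 10 × 0.407 + 10 × 0.553 = 9.6, and 9.6/400 = 2.4%, so it does not. The same data fall on opposite sides of the threshold.

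**Step 3: refusal unrelated to arm and outcome.** Let p be the true event rate and r the fraction refusing after the residual is known, without imputation.

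- 6.3 drops events and non-events alike: p(1 − r)/(1 − r) = p. The rates stay at 59.3% and 44.7%.
- 11.3 keeps events and drops only non-events: p/[p + (1 − p)(1 − r)]. With r = 0.049, free drainage is 0.593/0.980 = 60.5% and ICCAUT is 0.447/0.973 = 45.9%.

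The difference is −14.6 points either way.

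**Step 4: extreme one-sided cases.** Take 119/200 against 89/200 events (the planning rates rounded to counts), and assume that every refuser already had an observed event and none was a non-event. Pooled two-proportion z-test; difference is ICCAUT minus free drainage.

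| Observed events coded missing (free drainage / ICCAUT) | Missing left out | All-negative analysis |
|---|---|---|
| 0 / 0 (11.3 coding) | −15.0, p = 0.003 | −15.0, p = 0.003 |
| 9 / 9 | −15.7, p = 0.002 | −15.0, p = 0.003 |
| 9 / 0 | −13.1, p = 0.010 | −10.5, p = 0.036 |
| 0 / 9 | −17.6, p = 0.0005 | −19.5, p = 0.0001 |
| 19 / 0 (4.75% missing) | −10.7, p = 0.036 | −5.5, p = 0.27 |

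For example, 9 / 0 with missing left out is 89/200 − 110/191 = 44.5% − 57.6% = −13.1; all-negative, it is 44.5% − 110/200 = −10.5. These rows are bounds under a strong assumption, not expected effects.

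**The case against.** The strongest reply is that the analysis rule is already settled. The dedicated missing-data section and the SAP agree, the SAP carries only that rule, and an analyst who follows it keeps the event. This stands, and it is the main reason the point is minor.

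Second, the trigger in 6.3 names both components, and its stated purpose is to avoid losing the endpoint. It can be read as refusal of the whole assessment, in which case nothing has been observed and there is no conflict. That reading is possible, but the text does not say so, and partial refusal would then have no rule in 6.3.

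Third, a reader might infer that the residual is lost at data entry, because 6.3 asks only for other data to be recorded. The documents do not support this. Section 12.1 lists the first-void residual among the secondary as well as the primary outcome measures, and requires full CRF recording for every randomised patient. Section 2.2.2 makes a residual above 200 ml a secondary endpoint. Section 12.2 has endpoint data entered within two days of catheter removal. Unless use of the data is refused, the event can be re-derived.

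Fourth, a reader might infer a fall in an arm's rate by removing event refusers alone: 5 in ICCAUT gives (89.4 − 5)/195 = 43.3%, which is 1.4 points lower. That leaves the non-event refusers in the denominator. At 44.7%, 5 event refusers imply about 5/0.447 = 11.2 refusers. Coding under 6.3 then gives 84.4/188.8 = 44.7%, no fall; 11.3 without imputation gives 89.4/193.8 = 46.1%.

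Finally, patients and nurses are unblinded (5.2), so unequal refusal is possible. But the residual is measured after clamping has ended, and the documents offer no evidence that refusal differs by arm.

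**Conclusion.** The inconsistency is real and is in the current text. Read as written, 6.3 gives an endpoint status that is wrong by the plan's own definition whenever a positive component precedes the refusal. The consequences are a wrong missing count against the 5% trigger and an observed event treated as a non-event in the all-negative analysis.

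The effect on the risk difference is probably small. It is nil to one decimal if refusal is unrelated to arm and outcome, and 0.7 points or less with 9 observed events coded missing in each arm. It becomes material only if such refusals fall mainly in one arm, and nothing in the documents gives their number or direction. All sizes rest on the planning rates and on every event being visible before refusal.

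The documents do not support the stronger statements that events are irrecoverably erased or that an arm's rate would fall by a point or more. This is a minor inconsistency between sections, not a design choice.

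**What to change.** Amend protocol 6.3 to say that refusal of follow-up makes only the unobserved component missing; that residual and catheterisation data obtained before refusal are kept unless the patient refuses their use; and that endpoint status is derived under 11.3.1 and SAP 6.3.1 at any missing rate.

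Before analysis, check that no patient coded missing under 6.3 has a recorded residual above 100 ml or a recorded secondary catheterisation, restore the status of any who do, and only then compute the missing rate against 5%. Step 3 shows that 11.3 without imputation raises both arms' rates slightly; that is a property of the chosen rule and not a reason to leave the two sections in conflict.

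The cost is one sentence, a note to the research coordinator and a check of the affected records. No new procedures are needed and the sample size is unchanged. With 362 of 400 patients enrolled when the SAP was written (SAP 2.1), the check can be done before the final analysis.

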6.4 Protocol deviations

Researchers participating in the experiment will follow the experimental requirements for the corresponding operations and data recording. Any events that deviate from the original trial protocol must be recorded with the time of occurrence and specific reasons, and any deviations from the trial protocol must be explained.

7. Evaluation

7.1 Efficacy evaluation

The efficacy evaluation methods for different interventions include, but are not limited to: postoperative assessment of symptoms and signs, postoperative ultrasound assessment of the urinary system, postoperative evaluation of urination-related parameters, postoperative urinalysis and urine culture assessment, and postoperative surveys on urination function-related questionnaires.

7.2 Safety evaluation

7.2.1 Baseline vital signs and symptoms

When conducting a safety assessment, it is first necessary to understand the baseline vital signs and symptoms of the test subjects. This includes measuring their

body temperature, pulse, respiratory rate, and blood pressure, while noting any specific symptoms such as dizziness, nausea, vomiting, etc. Preoperative hematological examinations and imaging studies should be completed, along with preoperative urinalysis, urine culture, and preoperative voiding function questionnaire assessments. Additionally, the patient's medical history must be clarified and cross-checked against the trial's inclusion and exclusion criteria one by one to ensure that the patient population has no surgical contraindications and fully meets the enrollment criteria. These baseline data will serve as reference indicators for the assessment.

7.2.2 Laboratory examinations

The continuity indicators describe the measured values of each research subject after surgery and the change values relative to the preoperative baseline. The laboratory indicators are divided into low, normal, and high according to the normal value range. Describe the situations where the values change from normal or high at baseline to low after baseline, and where the values change from normal or low at baseline to high after baseline. The low or high values after baseline are calculated using the minimum or maximum observed value after baseline. Doctors will evaluate these abnormal indicators to determine whether their abnormalities have clinical significance. Describe the proportion of "abnormal and clinically significant" among the subjects with abnormal changes.

